6.9.1. Rescue Medicine

There is no rescue therapy to reverse the AEs observed with PF-07817883. Standard medical supportive care must be provided to manage the AEs.

7. DISCONTINUATION OF STUDY INTERVENTION AND PARTICIPANT DISCONTINUATION/WITHDRAWAL

7.1. Discontinuation of Study Intervention

It may be necessary for a participant to permanently discontinue study intervention. Reasons for permanent discontinuation of study intervention include the following:

- AE requiring discontinuation in investigator's view;
- Pregnancy.

If study intervention is permanently discontinued, the participant will not remain in the study for further evaluation. See the SoA for data to be collected at the time of discontinuation of study intervention.

7.1.1. Potential Cases of Acute Kidney Injury

Participants exposed to IMP demonstrating transient or sustained increase in Screat (with decrease in Screat-based eGFR or eCrCl) require expedited evaluation to differentiate AKI from DICI. DICI is defined as transporter-mediated effect related to altered renal tubular creatinine handling without histological injury.

AKI may be due to one or more types of injury, including DIKI. Differentiation of DIKI from other causes of AKI and from DICI may require clinical, radiographic, histopathologic, and laboratory assessments, as well as nephrology consultation.

Follow-up Assessments

The participant should return to the site for evaluation as soon as possible, preferably within 48 hours of awareness of the abnormal results.

Evaluation should include physical examination, laboratory tests, detailed medical and surgical history, review of all medications (including recreational drugs and supplements [herbal]), family history, sexual history, travel history, blood transfusion, and potential occupational exposure to chemicals.

Laboratory assessments should include simultaneous serum cystatin C (Scys) and serum creatinine (Screat) tests. Estimates of eGFR, eCrCl and Screat-based eGFR and combined Screat-Scys-based eGFR should also be derived using the appropriate equation described in Appendix 6.

Assessments of urine albumin-to-creatinine ratio or urine volume may also be performed as appropriate.

If appropriate, nephrology consultation may be recommended to facilitate differentiation of renal parenchymal disease, pre-renal azotemia, and post-renal obstruction.

Differentiating Acute Kidney Injury from DICI

A confirmed Screat increase is defined as:

- (i) ≥0.3 mg/dL (≥26.5 μmol/L) within 48 hours OR
- (ii) confirmed Screat increase ≥1.5 times baseline (known or suspected to have occurred within the prior 7 days).

Based on the assessments performed, suspected AKI (including DIKI) may be differentiated from DICI as follows.

Adult participants

	AKI (including DIKI) Any one of the below	DICI
Scys & Screat	Simultaneous, confirmed serum cystatin C (Scys) increase and confirmed Screat increase	Confirmed Screat increase without confirmed increase in reflex Scys AND
eGFR	Decrease in Screat-based eGFR and combined Screat-Scys-based eGFR (when available)	Confirmed Screat-based eGFR decrease without confirmed combined Screat-Scys-based eGFR decrease.
Albuminuria or proteinuria	Confirmed albuminuria increase (see Appendix 6 for Grades A1 to A3 quantitation)	
Urine volume	Urine volume <0.5 mL/kg/h for 6 consecutive hours	

Regardless of the presence or absence of increase in Screat, DIKI and other causes of AKI may be suspected if either there is (i) new-onset or worsening albuminuria or proteinuria are detected.

All confirmed cases of clinically relevant decrease in kidney function should be considered potential cases of DIKI if no other reason for the kidney function abnormalities has been found.

7.1.2. ECG Changes

A participant who meets either bulleted criterion based on the average of triplicate ECG readings will be withdrawn from the study intervention.

- QTcF >500 ms.
- Change from baseline: QTcF >60 ms and QTcF >450 ms.

If a clinically significant finding is identified (including, but not limited to, changes from baseline in QTcF after enrollment), the investigator or qualified designee will determine if the participant can continue in the study and if any change in participant management is needed. This review of the ECG printed at the time of collection must be documented. Any new clinically relevant finding should be reported as an AE.

7.2. Participant Discontinuation/Withdrawal From the Study

A participant may withdraw from the study at any time at their own request. Reasons for discontinuation from the study include the following:

- Refused further follow-up;
- Lost to follow-up;
- Death;
- Study terminated by sponsor;
- Investigator's decision;
- Pregnancy.

At the time of discontinuing from the study, if possible, an early discontinuation visit should be conducted. See the SoA for assessments to be collected at the time of study discontinuation and follow-up and for any further evaluations that need to be completed.

The early discontinuation visit applies only to participants who are enrolled/randomized and then are prematurely withdrawn from the study. Participants should be questioned regarding their reason for withdrawal.

The participant will be permanently discontinued from the study intervention and the study at that time.

If a participant withdraws from the study, they may request destruction of any remaining samples taken and not tested, and the investigator must document any such requests in the site study records and notify the sponsor accordingly.

If the participant withdraws from the study and also withdraws consent (see Section 7.2.1 for disclosure of future information, no further evaluations will be performed and no additional data will be collected. The sponsor may retain and continue to use any data collected before such withdrawal of consent.

7.2.1. Withdrawal of Consent

Participants who request to discontinue receipt of study intervention will remain in the study and must continue to be followed for protocol-specified follow-up procedures. The only exception to this is when a participant specifically withdraws consent for any further contact with them or persons previously authorized by the participant to provide this information. Participants should notify the investigator in writing of the decision to withdraw consent from future follow-up, whenever possible. The withdrawal of consent should be explained in detail in the medical records by the investigator, as to whether the withdrawal is only from further receipt of study intervention or also from study procedures and/or posttreatment study follow-up, and entered on the appropriate CRF page. In the event that vital status (whether the participant is alive or dead) is being measured, publicly available information should be used to determine vital status only as appropriately directed in accordance with local law.

7.3. Lost to Follow-Up

A participant will be considered lost to follow-up if the participant repeatedly fails to return for scheduled visits and is unable to be contacted by the study site.

The following actions must be taken if a participant fails to return to the clinic for a required study visit:

- The site must attempt to contact the participant and reschedule the missed visit as soon as possible. Counsel the participant on the importance of maintaining the assigned visit schedule and ascertain whether the participant wishes to and/or should continue in the study;
- Before a participant is deemed lost to follow-up, the investigator or designee must
 make every effort to regain contact with the participant (where possible, 3 telephone
 calls and, if necessary, a certified letter to the participant's last known mailing
 address or local equivalent methods). These contact attempts should be documented
 in the participant's medical record;
- Should the participant continue to be unreachable, the participant will be considered to have withdrawn from the study.

8. STUDY ASSESSMENTS AND PROCEDURES

8.1. Administrative and Baseline Procedures

The investigator (or an appropriate delegate at the investigator site) must obtain a signed and dated ICD before performing any study-specific procedures.

Study procedures and their timing are summarized in the SoA. Protocol waivers or exemptions are not allowed.

Adherence to the study design requirements, including those specified in the SoA, is essential and required for study conduct.

All screening evaluations must be completed and reviewed to confirm that potential participants meet all eligibility criteria. The investigator will maintain a screening log to record details of all participants screened and to confirm eligibility or record reasons for screening failure, as applicable.

Participants will be screened within 28 days prior to administration of the study intervention to confirm that they meet the study population criteria for the study. If the time between screening and dosing exceeds 28 days as a result of unexpected delays (eg, delayed drug shipment), then participants do not require rescreening if the laboratory results obtained prior to first dose administration meet eligibility criteria.

A participant who qualified for this protocol but did not enroll from an earlier cohort/group may be used in a subsequent cohort/group without rescreening, provided laboratory results obtained prior to the first dose administration meet eligibility criteria for this study. In addition, other clinical assessments or specimen collections, eg, retained research samples, may not need to be repeated, as appropriate.

Every effort should be made to ensure that protocol-required tests and procedures are completed as described. However, it is anticipated that from time to time there may be circumstances outside the control of the investigator that make it unfeasible to perform the test. In these cases, the investigator must take all steps necessary to ensure the safety and well-being of the participant. When a protocol-required test cannot be performed, the investigator will document the reason for the missed test and any corrective and preventive actions that they have taken to ensure that required processes are adhered to as soon as possible. The study team must be informed of these incidents in a timely manner.

If an IV catheter is utilized for blood sample collections, ECGs and vital sign assessments (pulse rate and BP) should be collected prior to the insertion of the catheter.

For samples being collected and shipped, detailed collection, processing, storage, and shipment instructions and contact information will be provided to the investigator site prior to initiation of the study.

The total blood sampling volume for individual participants in this study is approximately 270 mL. The actual collection times of blood sampling may change. Additional blood

samples may be taken for safety assessments at times specified by Pfizer, provided the total volume taken during the study does not exceed 550 mL during any period of 56 consecutive days.

To prepare for study participation, participants will be instructed on the information in the Lifestyle Considerations and Concomitant Therapy sections of the protocol.

8.1.1. Baseline Procedures

8.1.1.1. Medical History

A detailed medical history will be reviewed and recorded at screening and updated on admission. This will include detailed medical history as well as a history of prior illegal drug, alcohol, and tobacco use within 60 days prior to enrollment. If the participants are discharged between the periods, medical history may be updated.

8.1.1.2. Demographics

Participants' race, ethnicity, age, gender, height, and weight will be recorded at screening.

8.2. Efficacy Assessments

Efficacy parameters are not evaluated in this study.

8.3. Safety Assessments

Planned time points for all safety assessments are provided in the SoA. Unscheduled safety measurements may be obtained at any time during the study to assess any perceived safety issues.

8.3.1. Vital Signs

8.3.1.1. Blood Pressure and Pulse Rate

Supine BP will be measured with the participant's arm supported at the level of the heart, and recorded to the nearest mm Hg after approximately 5 minutes of rest. The same arm (preferably the dominant arm) will be used throughout the study. Participants should be instructed not to speak during measurements.

The same properly sized and calibrated BP cuff will be used to measure BP each time. The use of an automated device for measuring BP and pulse rate is acceptable; however, when done manually, pulse rate will be measured in the brachial/radial artery for at least 30 seconds. When the timing of these measurements coincides with a blood collection, BP and pulse rate should be obtained prior to the nominal time of the blood collection.

Additional collection times, or changes to collection times, of BP and pulse rate will be permitted, as necessary, to ensure appropriate collection of safety data.

Any untoward vital sign findings that are identified during the active collection period and meet the definition of an AE or SAE (Appendix 3) must be reported according to the processes in Sections 8.4.1 to 8.4.3.

8.3.2. Physical Examinations

A complete physical examination will include, at a minimum, head, ears, eyes, nose, mouth, skin, heart and lung examinations, lymph nodes, and gastrointestinal, musculoskeletal, and neurological systems.

A brief physical examination will include, at a minimum, assessments of general appearance, the respiratory and cardiovascular systems, and participant-reported symptoms.

Physical examinations may be conducted by a physician, trained physician's assistant, or nurse practitioner as acceptable according to local regulation.

Height and weight will also be measured and recorded as per the SoA. For measuring weight, a scale with appropriate range and resolution is used and must be placed on a stable, flat surface. Participants must remove shoes, bulky layers of clothing, and jackets so that only light clothing remains. They must also remove the contents of their pockets and remain still during measurement of weight.

Physical examination findings collected during the study will be considered source record and will not be required to be reported, unless otherwise noted. Any untoward physical examination findings that are identified during the active collection period and meet the definition of an AE or SAE (Appendix 3) must be reported according to the processes in Sections 8.4.1 to 8.4.3.

8.3.3. Electrocardiograms

Standard 12-lead ECGs will be collected at times specified in the SoA section of this protocol using an ECG system that automatically calculates the HR and measures PR, QT, QTcF, and QRS intervals. All scheduled ECGs should be performed after the participant has rested quietly for at least 5 minutes in a supine position.

To ensure safety of the participants, a qualified individual at the investigator site will make comparisons to baseline measurements. Additional ECG monitoring will occur if a) a postdose QTcF interval is increased by ≥60 ms from the baseline and is >450 ms; or b) an absolute QT value is ≥500 ms for any scheduled ECG. If either of these conditions occurs, then 2 additional ECGs will be collected approximately 2 to 4 minutes apart to confirm the original measurement. If the QTcF values from these repeated ECGs remain above the threshold value, then a single ECG must be repeated at least hourly until QTc values from 2 successive ECGs fall below the threshold value that triggered the repeat measurement.

If a) a postdose QTcF interval remains ≥60 ms from the baseline and is >450 ms; or b) an absolute QT value is ≥500 ms for any scheduled ECG for greater than 4 hours (or sooner, at the discretion of the investigator); or c) QTcF value get progressively longer, the participant should undergo continuous ECG monitoring. A cardiologist should be consulted if QTcF values do not return to less than the criteria listed above after 8 hours of monitoring (or sooner, at the discretion of the investigator).

In some cases, it may be appropriate to repeat abnormal ECGs to rule out improper lead placement as contributing to the ECG abnormality. It is important that leads be placed in the same positions each time in order to achieve precise ECG recordings. If a machine-read QTc value is prolonged, as defined above, repeat measurements may not be necessary if a qualified medical provider's interpretation determines that the QTcF values are in the acceptable range.

ECG values of potential clinical concern are listed in Appendix 7.

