1.3. Schedule of Activities

The SoA table provides an overview of the protocol visits and procedures. Refer to the STUDY ASSESSMENTS AND PROCEDURES section of the protocol for detailed information on each procedure and assessment required for compliance with the protocol.

The investigator may schedule visits (unplanned visits) in addition to those listed in the SoA table, in order to conduct evaluations or assessments required to protect the well-being of the participant.

Table 1. Schedule of Activities

Visit Identifier Abbreviations used in this table may be found in Section 10.9	Screening			For each of Period 1-4									FU	ET	Notes
Days Relative to Day 1	Day -28 to Day -2	Day -1		Day 1							Day 2	Day 3	28- 35 days		F/U activities only in the last period. F/U may occur via telephone contact, must occur 28-35 days after the final dose of study intervention. Day -1 activities only before Period 1 Day 1.
Planned hours Post dose			0	0.5	1	2	4	6	8	12	24	48			
Informed consent	X														
Inclusion/exclusion criteria	X	X													Period 1 only
CRU Confinement		X	\rightarrow	\rightarrow	\rightarrow	\rightarrow	→	-	→	\rightarrow	→	X			
Medical/medication history (update)	X	X					Г								
Demography (including weight and height)	X														Refer to Section 8.1.1.2
Contraception check	X	X										X	X	X	Day 3 performed only at discharge from CRU
12-lead ECG (single)	х		Х									X		Х	Day 1 performed pre-dose Day 1 not required in Periods 2-4 Day 3 only in last period
Vital signs (BP/PR)	Х		Х									X		X	Day 1 performed pre-dose Day 3 only in the last period Refer to Section 8.3.1

Table 1. Schedule of Activities

Visit Identifier Abbreviations used in	Screening			For each of Period 1-4									FU	ET	Notes
this table may be found in Section 10.9															
Days Relative to Day 1	Day -28 to Day -2	Day -1		Day 1							Day 2	Day 3	28- 35 days		 F/U activities only in the last period. F/U may occur via telephone contact, must occur 28-35 days after the final dose of study intervention. Day -1 activities only before Period 1 Day 1.
Planned hours Post dose			0	0.5	1	2	4	6	8	12	24	48			
COVID-19 test/ procedures	X	X													 COVID-19 test to meet inclusion on admission. Other COVID-19 related procedures per local regulations.
PE	X	X												X	 PE will be performed at screening or admission. PE at ET visit only at PI's discretion
Serious and nonserious AE monitoring	X	→	→	→	→	→	^	-	→	→	→	→	X	Х	
Urine sample for:															

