10.7. Appendix 7: ECG Findings of Potential Clinical Concern

ECG Findings That May Qualify as AEs

- Marked sinus bradycardia (rate <40 bpm) lasting minutes.
- New PR interval prolongation >280 ms.
- New prolongation of QTcF to >480 ms (absolute).
- New prolongation of QTcF by >60 ms from baseline.
- New-onset atrial flutter or fibrillation, with controlled ventricular response rate: ie, rate <120 bpm.
- New-onset type I second-degree (Wenckebach) AV block of >30-second duration.
- Frequent PVCs, triplets, or short intervals (<30 seconds) of consecutive ventricular complexes.

ECG Findings That May Qualify as SAEs

- QTcF prolongation >500 ms.
- Absolute value of QTcF > 450 ms AND QTcF change from baseline >60 ms.
- New ST-T changes suggestive of myocardial ischemia.
- New-onset LBBB (QRS complex>120 ms).
- New-onset right bundle branch block (QRS complex>120 ms).
- Symptomatic bradycardia.
- Asystole
 - In awake, symptom-free participants in sinus rhythm, with documented asystolic pauses ≥3 seconds or any escape rate <40 bpm, or with an escape rhythm that is below the AV node;
 - In awake, symptom-free participants with atrial fibrillation and bradycardia with 1 or more asystolic pauses of at least 5 seconds or longer.
- Atrial flutter or fibrillation, with rapid ventricular response rate: rapid = rate
 >120 bpm.

- Sustained supraventricular tachycardia (rate >120 bpm) ("sustained" = short duration with relevant symptoms or lasting >1 minute).
- Ventricular rhythms >30 seconds' duration, including idioventricular rhythm (HR <40 bpm), accelerated idioventricular rhythm (HR >40 bpm to <100 bpm), and monomorphic/polymorphic ventricular tachycardia (HR >100 bpm [such as torsades de pointes]).
- Type II second-degree (Mobitz II) AV block.
- Complete (third-degree) heart block.

ECG Findings That Qualify as SAEs

- Change in pattern suggestive of new myocardial infarction.
- Sustained ventricular tachyarrhythmias (>30-seconds duration).
- Second- or third-degree AV block requiring pacemaker placement.
- Asystolic pauses requiring pacemaker placement.
- Atrial flutter or fibrillation with rapid ventricular response requiring cardioversion.
- Ventricular fibrillation/flutter.
- At the discretion of the investigator, any arrhythmia classified as an adverse experience.

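### The absolute 500 ms trigger for repeat ECGs in Protocol 8.3.3 is on uncorrected QT, so a narrow band of QTcF above 500 ms has no mandated confirmatory ECG

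*Protocol*

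**What the plan says.** Section 8.3.3 of the Protocol has a sequence of steps, and the interval it uses changes along the way.

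- **Repeat ECGs.** Two further ECGs, 2 to 4 minutes apart, are taken if (a) post-dose QTcF has risen by 60 ms or more from baseline and is above 450 ms, or (b) "an absolute QT value is ≥500 ms for any scheduled ECG".
- **Confirmation.** The next step applies "If the QTcF values from these repeated ECGs remain above the threshold value".
- **Hourly ECGs.** These continue "until QTc values from 2 successive ECGs fall below the threshold value that triggered the repeat measurement".
- **Continuous monitoring.** The same clauses (a) and (b) apply, with (b) again on uncorrected QT, plus a clause (c) for progressive QTcF lengthening.
- **Referral.** "A cardiologist should be consulted if QTcF values do not return to less than the criteria listed above after 8 hours of monitoring".

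Elsewhere the 500 ms limit is on QTcF. Section 7.1.2 withdraws a participant from study intervention, "based on the average of triplicate ECG readings", for QTcF above 500 ms, or for a rise above 60 ms with QTcF above 450 ms. Appendix 7 lists "QTcF prolongation >500 ms" among findings that may qualify as SAEs. The severe category in Protocol 9.3.5.1 and SAP Appendix 2 is also QTcF above 500 ms.

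Scheduled ECGs are single. The 12-lead ECG row of the Schedule of Activities notes "Day 1 not required in Periods 2-4 Day 3 only in last period", so the scheduled post-dose ECGs are those on Day 3 of the last period and at early termination.

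**The concern.** The rule that produces a confirmatory ECG does not match the limits it serves. Section 7.1.2 needs an average of three readings, scheduled ECGs are single, and the two extra ECGs in 8.3.3 are the only mandated route to three. Clause (a) covers the second 7.1.2 criterion. Nothing in 8.3.3 covers the first, because clause (b) looks at QT. At heart rates above 60 bpm Fridericia's correction makes QTcF larger than QT, so QTcF can pass 500 ms while QT stays below it.

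There is also a gap in wording. When (b) fires on QT, the following steps compare a corrected interval with a threshold that was set on an uncorrected one. The natural reading is 500 ms, but the text does not say so.

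At stake is whether a value that the protocol itself lists as a possible SAE must be confirmed before the participant leaves the unit. Day 3 is the discharge day in the last period, and the later follow-up may be by telephone.

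**Working it through.** There is no figure in the plan to reproduce. The check is whether triggers (a) and (b) together cover every QTcF above 500 ms.

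**Inputs**
- Trigger (a): QTcF rise ≥60 ms and QTcF >450 ms (Protocol 8.3.3).
- Trigger (b): QT ≥500 ms (Protocol 8.3.3).
- QTcF = QT / (60/HR)^(1/3) (SAP 3.2.4).
- Baseline: last value before dosing on Period 1 Day 1 (SAP 3.2.4).
- Assumption: baseline QTcF ≤450 ms, the eligibility limit in Protocol 5.2, criterion 9.

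**When (a) misses.** For QTcF above 500 ms, (a) fails only if QTcF − baseline < 60. That needs baseline > 500 − 60 = 440 ms. With baseline ≤450 ms it also needs QTcF < 450 + 60 = 510 ms.

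| Baseline QTcF (ms) | QTcF values missed by (a), whole ms |
|---|---|
| 450 | 501–509 |
| 448 | 501–507 |
| 445 | 501–504 |
| 442 | 501 |
| 441 or lower | none |

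(At baseline 441 a fractional QTcF between 500 and 501 ms is still missed; at 440 or lower nothing is.)

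**When (b) misses.** QT = QTcF × (60/HR)^(1/3) is below 500 ms when HR > 60 × (QTcF/500)^3:
- QTcF 501: 60 × (501/500)^3 = 60.4 bpm
- QTcF 505: 60 × (505/500)^3 = 61.8 bpm
- QTcF 509: 60 × (509/500)^3 = 63.3 bpm

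**Examples in which neither fires**
- Baseline 448, HR 75, QT 469: QTcF = 469/(60/75)^(1/3) = 505.2, rise 505.2 − 448 = 57.2 ms.
- Baseline 442, HR 70, QT 476: QTcF = 476/(60/70)^(1/3) = 501.1, rise 501.1 − 442 = 59.1 ms.

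**Coverage.** Over whole-number baselines 400–450 ms, HR 40–100 bpm and QT 380–599 ms, 1932 combinations with QTcF above 500 ms fire neither trigger. All have baseline 441–450 ms and HR 61 bpm or higher. If (b) is extended to QT or QTcF ≥500 ms, the count is 0. This shows coverage, not probability.

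**Why add and not replace.** QT 500 at HR 50 gives QTcF = 500/(60/50)^(1/3) = 470.5, a rise of 50.5 ms from baseline 420. It triggers repeats now through (b). If QTcF replaced QT, nothing would fire.

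**If the assumption fails.** The entry limit is not explicitly re-applied to the Period 1 Day 1 ECG. A baseline of 455 ms would widen the band to 455 + 60 − 500 = 15 ms, and 460 ms to 20 ms.

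**The case against.** Several points can be made for leaving the text alone.

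- **The QT trigger is deliberate.** Protocol 9.3.5.1 and SAP 6.2.4 tabulate uncorrected QT above 500 ms. This stands, and it is a reason to keep QT. It does not explain the absence of QTcF.
- **Other safeguards exist.** Unscheduled measurements are allowed (8.3), abnormal ECGs may be repeated (8.3.3), AEs are followed with further tests as medically indicated (8.4.3, 10.3.3), Appendix 7 flags QTcF above 480 and 500 ms, and 7.1.2 requires a documented review of any clinically significant ECG finding. A QTcF of 501–509 ms would very probably prompt action. But these rest on judgement, and the SAP 6.2.4 listing of QTcF above 500 ms comes only at reporting.
- **The 8.3.3 repeats also yield to judgement.** They may be skipped if a qualified reader finds QTcF acceptable. That exception does not help when the over-read confirms QTcF above 500 ms.
- **The threshold is already implied.** The stopping rule points back to the triggering value, which for (b) is 500 ms. This largely stands; the added sentence only makes it explicit.
- **Little drug remains.** The Day 3 ECG is at 48 hours, and Protocol 4.2 judges the washout sufficient to bring concentrations below 5% of Cmax. This stands and lowers the practical weight. An early-termination ECG could fall nearer to dosing.
- **Adding QTcF leaves the QT limb weak.** At QT 505 and HR 50, QTcF is 475.2 ms, so repeats judged on QTcF 500 ms stop at once. True, but the same happens under the present text, which already judges repeats on QTcF.

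**Conclusion.** The concern holds, as a minor safety-monitoring inconsistency. No clause in 8.3.3 fires on an absolute QTcF of 500 ms, and nothing else in the documents requires a repeat at that value. The uncovered band is at most 10 ms wide, and only for baselines above 440 ms and heart rates above about 60 to 63 bpm, assuming baseline does not exceed 450 ms.

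The documents give no frequency for such readings; in about 12 healthy adults they are likely to be rare. No dosing decision follows: the Day 3 ECG comes after the final dose, and participants at early termination are permanently off study intervention (Protocol 7.2). What is missing is the mandated confirmation of a possible SAE.

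**What to change.** In Section 8.3.3, insert *or QTcF* after *QT* in clause (b), in both the repeat-ECG rule and the continuous-monitoring rule. Add one sentence: when clause (b) fired, the repeat ECGs and the check for stopping hourly ECGs are judged against QTcF 500 ms. Leave clause (a), the ECG schedule, Section 7.1.2 and Appendix 7 unchanged.

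The change removes no existing trigger. It costs an edit to two clauses, one new sentence in one section, and at most a few extra repeat ECGs.
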